9.5 Pharmacokinetics and Immunogenicity

The PK of BMS-986207 will be derived from serum concentration versus time data when appropriate. The PK parameters that will be assessed, following the intensive PK collection, are shown in Table 9.5-1.

Table 9.5-1: Pharmacokinetic Parameters

Parameters	Definition
Cmax	Maximum observed serum concentration
Tmax	Time of maximum observed serum concentration
AUC(0-T)	Area under the serum concentration-time curve from time zero to time of last quantifiable concentration
AUC(TAU)	Area under the concentration-time curve in one dosing interval
Parameters that may potentially be assessed following the dose administration in Cycle 2 Day 1	
Ctau	Observed concentration at the end of a dosing interval
CLT	Total body clearance
Css-avg	Average concentration over a dosing interval (AUC[TAU]/tau)
AI_TAU	Ratio of an exposure measure at steady state to that after the first dose (exposure measure includes AUC[TAU])
T-HALFeff	Effective elimination half-life that explains the degree of accumulation observed for a specific exposure measure (exposure measure includes AUC[TAU])
Parameter to be reported separately	

Individual participant PK parameter values will be derived by noncompartmental methods by a validated PK analysis program. Actual times will be used for the analyses.

[Table 9.5-2](#), [Table 9.5-3](#), and [Table 9.5-4](#) list the sampling schedule to be followed for the assessment of PK and immunogenicity. Further details of blood collection and processing will be provided to the site in the Laboratory Manual.

All predose samples should preferably be taken within 30 minutes before the start of any dose infusion. In Part 1C and 2C, as shown in [Table 9.5-4](#) end-of-infusion (EOI) PK samples for BMS-986207, nivolumab, and ipilimumab should be taken immediately following the last drug infusion (preferably within 5 minutes after end of the infusion) on the contralateral arm (ie, the arm not used for the infusion). Since the EOI PK sample is drawn with the intent of accurately estimating the maximum concentration (Cmax) of the drug, draw the EOI-PK after all the study drug has been

infused. If the site infuses drug without a flush, then collect the EOI-PK sample within approximately 5 minutes after end of infusion. If a flush is administered to clear the IV lines of the drug and to ensure delivery of the entire drug dose, then draw the EOI-PK sample within approximately 5 minutes after the end of the flush. If the end of infusion is delayed to beyond the nominal infusion duration, the collection of this sample should also be delayed accordingly. On-treatment PK samples are intended to be drawn relative to actual dosing days. For Part 1A, 1B, 2A, and 2B, EOI PK samples for BMS-986207 or nivolumab should be taken following the instructions noted in [Table 9.5-2](#) and [Table 9.5-3](#).

If a dose occurs on a different day within the cycle due to delays or minor schedule adjustments, PK and ADA samples should be adjusted accordingly. If it is known that a dose is going to be delayed, then the predose sample should be collected just prior to the delayed dose. However, if a predose sample is collected but the dose is subsequently delayed, an additional predose sample should be collected. ‘Event Kit - Dose Delay’ should be used in the event that a predose PK sample was obtained and the participant is not dosed on that same day. Following consensus of the Investigator and the BMS Medical Monitor, an additional PK and/or ADA sample may be taken following a SAE or important medical event using an ‘Event Kit - AE’. Further details of sample collection, processing, and shipment will be provided in the Laboratory Manual.

Table 9.5-2: Pharmacokinetic and Immunogenicity Sampling Schedule for BMS-986207 [REDACTED] in q2w Dose Panels in Part 1A, 1B, 2A, and 2B

Study Day of Sample Collection (1 cycle = 8 weeks)	Event	Time (Relative to Start of Infusion) Hour: Min	BMS-986207 Blood Sample (All Participants)	[REDACTED]	BMS-986207 ADA Samples (All participants)	[REDACTED]
C1D1	Predose	00.00	X		X	
	EOI ^b	30 to 60 min	X			
		4:00	X			
C1D2		24:00	X			
C1D5 ^c		96:00	X			
C1D8 ^d		168:00	X			
C1D15	Predose ^a	00: 00	X		X	
	EOI ^b	30 to 60 min	X			
		4:00	X			
C1D29	Predose ^a	00: 00	X		X	
	EOI ^b	30 to 60 min	X			
C2D1	Predose ^a	00: 00	X			
	EOI ^b	30 to 60 min	X			
		4:00	X			
C2D2		24:00	X			
C2D5 ^c		96:00	X			
C2D8 ^d		168:00	X			
C2D15	Predose ^a	00: 00	X			
C2D29	Predose ^a	00: 00	X		X	

Table 9.5-2: Pharmacokinetic and Immunogenicity Sampling Schedule for BMS-986207 [REDACTED] in q2w Dose Panels in Part 1A, 1B, 2A, and 2B

Study Day of Sample Collection (1 cycle = 8 weeks)	Event	Time (Relative to Start of Infusion) Hour: Min	BMS-986207 Blood Sample (All Participants)	[REDACTED]	BMS-986207 ADA Samples (All participants)	[REDACTED]
C3D1	Predose ^a	00: 00	X	[REDACTED]	X	[REDACTED]
C3D29	Predose ^a	00: 00	X	[REDACTED]		[REDACTED]
C4D1	Predose ^a	00: 00	X	[REDACTED]	X	[REDACTED]
C5D1	Predose ^a	00: 00	X	[REDACTED]	X	[REDACTED]
EOT			X	[REDACTED]	X	[REDACTED]
30-day follow-up			X	[REDACTED]	X	[REDACTED]
60-day follow-up			X	[REDACTED]	X	[REDACTED]
PK SAE event	'PK EVENT Kit - AE' should be used when PK and/or ADA sample is taken following a SAE or important medical					
PK dose delay	'PK DELAY Kit - Dose Delay' should be used to collect an additional predose sample if a predose sample was already collected for the same visit but the dose was subsequently delayed					
Retreatment	PK/ADA sampling to be done predose on Day 1 of all cycles; @ EOT and 30 and 60 day followup visits. No dose delay PK sampling to be done in Retreatment					

Abbreviations: ADA, anti-drug antibody, BMS, Bristol-Myers Squibb; EOI, end of infusion, EOT, end of treatment

^a Predose: All predose samples for [REDACTED] BMS-986207 should be taken prior to the start of the [REDACTED] infusion. If the predose sample has been taken, however, the unscheduled, missing, or delayed dose occurs, an additional predose sample shall be taken.

^b EOI samples for both [REDACTED] BMS-986207 should be collected immediately following the infusion (preferably within 2 minutes of stopping the infusion). If the end of infusion is delayed to beyond the nominal infusion duration, the collection of this sample should also be delayed accordingly.

^c The 96:00 hour sample may be taken between 72:00 and 120:00 hours post dose

^d The 168:00 hour sample may be taken between 144:00 and 192:00 hours post dose

Table 9.5-3: Pharmacokinetic and Immunogenicity Sampling Schedule for BMS-986207 [REDACTED] in q4w Dose Panels in Parts 1A, 1B, 2A, and 2B

Study Day of Sample Collection (1 cycle = 8 weeks)	Event	Time (Relative to Start of Infusion) Hour: Min	BMS-986207 Blood Sample (All Participants)		BMS-986207 ADA Samples (All participants)	
C1D1	Predose	00.00	X		X	
	EOI ^b	30 to 60 min	X			
		4:00	X			
C1D2		24:00	X			
C1D5 ^c		96:00	X			
C1D8 ^d		168:00	X			
C1D15		336:00	X			
C1D22		504:00	X			
C1D29	Predose ^a	00: 00	X			
	EOI ^b	30 to 60 min	X			
C2D1	Predose ^a	00: 00	X		X	
	EOI ^b	30 to 60 min	X			
C2D29	Predose ^a	00:00	X			
	EOI	30 to 60 min	X			
C3D1	Predose ^a	00: 00	X		X	
	EOI ^b	30 to 60 min	X			
		4:00	X			
C3D2		24:00	X			
C3D5 ^c		96:00	X			

Table 9.5-3: Pharmacokinetic and Immunogenicity Sampling Schedule for BMS-986207 [REDACTED] in q4w Dose Panels in Parts 1A, 1B, 2A, and 2B

Study Day of Sample Collection (1 cycle = 8 weeks)	Event	Time (Relative to Start of Infusion) Hour: Min	BMS-986207 Blood Sample (All Participants)		BMS-986207 ADA Samples (All participants)	
C3D8 ^d		168:00	X			
C3D15		336: 00	X			
C3D22		504: 00	X			
C3D29	Predose ^a	00: 00	X			
C4D1	Predose ^a	00: 00	X		X	
C5D1	Predose ^a	00: 00	X		X	
EOT			X		X	
30-day follow-up			X		X	
60-day follow-up			X		X	
PK SAE Event	'PK EVENT Kit - AE' should be used when PK and/or ADA sample is taken following a SAE or important medical					
PK Dose Delay	'PK DELAY Kit - Dose Delay' should be used to collect an additional predose sample if a predose sample was already collected for the same visit but the dose was subsequently delayed					
Retreatment	PK/ADA sampling to be done predose on Day 1 of all cycles; @ EOT and 30 and 60 day followup visits. No dose delay PK sampling to be done in Retreatment					

Abbreviations: ADA, anti-drug antibody, BMS, Bristol-Myers Squibb; EOI, end of infusion, EOT, end of treatment

^a Predose: All predose samples for [REDACTED] BMS-986207 should be taken prior to the start of the [REDACTED] infusion. If the predose sample has been taken, however, the unscheduled, missing, or delayed dose occurs, an additional predose sample shall be taken.

^b EOI samples for both [REDACTED] BMS-986207 should be collected immediately following the infusion (preferably within 2 minutes of stopping the infusion). If the end of infusion is delayed to beyond the nominal infusion duration, the collection of this sample should also be delayed accordingly.

^c The 96:00 hour sample may be taken between 72:00 and 120:00 hours post dose

^d The 168:00 hour sample may be taken between 144:00 and 192:00 hours post dose

**Table 9.5-4: Pharmacokinetic and Immunogenicity Sampling Schedule for BMS-986207, [REDACTED]
[REDACTED] in Parts 1C and 2C**

Study Day of Sample Collection (1 cycle = 6 weeks)	Event	Time Relative to [REDACTED] Dose Hour: Min	BMS-986207 PK Serum Sample	BMS-986207 (ADA) Serum Samples
C1D1	Predose ^a	00.00	X	X
	EOI ^b		X	
		4:00	X	
C1D2		24:00	X	
C1D5 ^c		96:00	X	
C1D8 ^d		168:00	X	
C1D15		336:00	X	
C1D22	Predose ^a	00:00	X	
C1D29 ^e		168:00	X	
C2D1	Predose ^a	00:00	X	X
C2D22	Predose ^a	00:00	X	
C3D1	Predose ^a	00:00	X	X
	EOI ^b		X	
		4:00	X	
C3D2		24:00	X	
C3D5		96:00	X	
C3D8		168:00	X	
C3D15		336:00	X	

**Table 9.5-4: Pharmacokinetic and Immunogenicity Sampling Schedule for BMS-986207, [REDACTED]
[REDACTED] in Parts 1C and 2C**

Study Day of Sample Collection (1 cycle = 6 weeks)	Event	Time Relative to [REDACTED] Dose Hour: Min	BMS-986207 PK Serum Sample	BMS-986207 (ADA) Serum Samples
C3D22	Predose ^a	00: 00	X	
C4D1	Predose ^a	00: 00	X	X
Every 4 cycles starting at Cycle 5 Day 1 until Cycle 17 (C5D1; C9D1; C13D1; C17D1)	Predose ^a	00: 00	X	X

Abbreviations: ADA, anti-drug antibody, BMS, Bristol-Myers Squibb; C, cycle; D, day; EOI, end of infusion; PK, pharmacokinetics.

^a Predose: All predose samples for [REDACTED] BMS-986207 should be taken prior to the start of the [REDACTED] infusion. If the predose sample has been taken, however, the unscheduled, missing, or delayed dose occurs, no additional predose sample shall be taken.

^b EOI samples for [REDACTED] BMS-986207 should be collected immediately following the last drug infusion (preferably within 5 minutes of after end of infusion) on the contralateral arm (i.e. the arm not for the infusion). Since the EOI PK sample is drawn with the intent of accurately estimating the maximum concentration (Cmax) of the drug, draw the EOI-PK when all the study drug has been infused. If the site infuses drug without a flush, then collect the EOI-PK sample within approximately 5 minutes after end of infusion. If a flush is administered to clear the IV lines of the drug and to ensure delivery of the entire drug dose, then draw the EOI-PK sample within approximately 5 minutes after end of the flush. If the end of infusion is delayed to beyond the nominal infusion duration, the collection of this sample should also be delayed accordingly.

^c The 96:00 hour sample may be taken between 72:00 and 120:00 hours post dose

^d The 168:00 hour sample may be taken between 144:00 and 192:00 hours post dose

^e PK sample collection for C1D29 is strongly recommended to be synchronized (collected on the day) with biopsy collection for C1D29.

[figure not shown]
The serum samples will be analyzed for BMS-986207 antibodies [REDACTED] ADA (anti-BMS-986207 [REDACTED]).

9.5.1 Pharmacokinetic Sample Analyses

Validated immunoassays will be used to measure concentrations of BMS-986207, [REDACTED] in serum.

9.5.2 Immunogenicity Sample Analysis

Validated immunoassays will be used to assay samples for the presence of, and measure titers of anti-BMS-986207, [REDACTED] antibodies in serum.

[figure not shown]
9.7 Pharmacogenomics

[figure not shown]
Circulation tumor DNA (ctDNA) and T cell Repertoire analysis may be performed to assess the association of these tumor-specific genetic features with clinical outcome. More details about these assays are described [REDACTED]

9.7.1 ADME Sampling

[figure not shown]
A whole blood sample will be drawn at baseline (Day 1) for potential analysis of DNA variants in absorption, distribution, metabolism and excretion (ADME)-related genes (Table 2-2, Appendix 7). Paxgene sampling will be performed in accordance with the Laboratory Manual. Further details of blood collection and processing will also be provided to the site in the Laboratory Manual.

10. STATISTICAL CONSIDERATIONS

10.1 Sample Size Determination

10.1.1 *Dose Escalation*

During the dose escalation phase, an adaptive dose escalation scheme (BLRM for monotherapy and BLRM-copula for combination therapy) employing the escalation with overdose control (EWOC) principle will be used. The method is fully adaptive, makes use of all the information available at the time of each dose assignment, not just data from the current dose level, and directly addresses the ethical need to control the probability of overdosing. The targeted toxicity rate in this study is in the range of [16%, 33%). The boundary is similar to the toxicity boundary used by a rule-based design (ie, 3 + 3 design) in that a minimum is set at 16% (~ 1 in 6) DLT rate and a maximum at 33% (~ 2 in 6) DLT rate. The use of the EWOC principle limits the risk of exposing patients in the next cohort to an unsafe dose by ensuring the posterior probability of the DLT rate exceeding 33% at any dose is capped at 30%.

The maximum number of participants treated will be 35 for each dose escalation part (BMS-986207 monotherapy [Part 1A], BMS-986207 in combination with nivolumab [Part 1B]). However, simulation studies with various scenarios show that the expected number of DLT-evaluable participants is no more than approximately 20. ([Appendix 12](#)).

Approximately 3 participants will be treated at the starting dose levels of BMS-986207 or BMS-986207 in combination with nivolumab. While the BLRM/BLRM-copula will use DLT information from the DLT period only, clinical assessment will take into consideration of the totality of available data including PK/█ from all treated participants encompassing monotherapy and combination therapy, in assigning a dose level for the next cohort of 3 participants. At least

6 DLT-evaluable participants will be treated at the MTD. At most 12 DLT-evaluable participants will be treated at each dose level. Additional participants (up to a total of 15) may be treated at or any dose level below the estimated MTD for further evaluation of safety, PK, [REDACTED] parameters as required.

The model-recommended MTD is the dose that satisfies the following three conditions:

- 1) The empirical posterior probability that the “DLT rate of 16% - <33%” is greater than a pre-specified value (i.e., 50%);
- 2) This probability needs to be the largest amongst the dose levels that satisfy the EWOC condition (i.e., the probability that the “DLT rate $\geq 33\%$ ” must be less than 30%);
- 3) Minimum number of participants (i.e., 6) were treated at this dose level.

The final recommended MTD/RP2D will be based on the recommendation from the BLRM/BLRM-copula and overall clinical assessment of all available safety, PK, [REDACTED] and efficacy data. Lower doses of BMS-986207 may be tested if none of the planned doses are found to be tolerable as monotherapy or in combination with nivolumab. Such decisions will be made after discussion and agreement between the Investigators and the BMS Medical Monitor.

10.1.2 Safety Evaluation Phase (Part 1C)

The safety of triplet therapy will be evaluated across the tumor types in up to approximately 18 treated participants per dose level who receive triplet therapy based on the number of DLTs observed. Assuming a DLT target of 30% (24%, 36%) the BOPN design framework will be used to guide decisions in this setting, including potential de-escalation to a lower dose of BMS-986207 in combination with both nivolumab and ipilimumab, if warranted by the observed results (see [Table 5.1.2.6-1](#)). In addition, calculations related to the risk of a BMS-986207 dose level selected as tolerable are shown expressed as a posterior probability of toxicity in [Section 5.1.2.2 \(Table 5.1.2.6-2\)](#).

10.1.3 Cohort Expansion

The purpose of cohort expansion is to gather additional safety, tolerability, preliminary efficacy, PK, [REDACTED] information regarding BMS-986207 alone or in combination with nivolumab. However, the sample size is strictly based on efficacy, specifically on the target ORR relative to historic response rate.

10.1.3.1 Cohort Expansion in Part 2A and Part 2B

Part 2A will be an expansion phase of the BMS-986207 monotherapy in participants with CRC at 1 dose level. Part 2B will be an expansion phase for BMS-986207 in combination with nivolumab in participants with CRC, HCC, and ovarian cancer. Each disease cohort expansion will be handled independently and there will be no multiplicity adjustment.

The Fleming 2-stage design framework will be used as a guide for the expansion cohorts in Parts 2A and 2B.^{42,43} The total sample size for each expansion cohort will be calculated to provide a reasonable false-positive rate (FPR) <10% and false-negative rate (FNR) < 10% based on

assumptions of true (target) and historic ORR for each indication. The assumed historic and target response rates may change over time and may need to be adjusted by the time when the response data from this study are available. The sample size and operational characteristics of using a 2-stage design, as an example, are provided in Table 10.1.3.1-1, although this is not used for statistical hypothesis testing. Using a 2-stage design provides an option to stop early for futility, as well as a signal of preliminary [REDACTED] activity for strong-go, early on. Enrollment may continue into Stage 2, while the planned number of participants for Stage 1 are followed for efficacy evaluable tumor assessments. There will be no stopping of a disease cohort for efficacy, although an early plan for the next stage of clinical development may be initiated. Sample sizes may need to be increased in order to explore differential responses between [REDACTED] expressed and nonexpressed groups.

Guided by Table 10.1.3.1-1, approximately 11 CRC participants will be treated with BMS-986207 monotherapy in Stage 1. Assuming the true response rate is 20% in this population when treated with BMS-986207 monotherapy, if there are 2 or more responses in 11 participants, it may trigger an expansion of the clinical development plan after careful evaluation of all available data including duration of response and safety profile. The probability to observe such a favorable response is approximately 68% if in fact the treatment is efficacious. If there is no response in 11 treated participants, the cohort may be stopped for futility. The probability of early stopping for futility is approximately 80% if in fact the treatment is inefficacious, eg, 2%. If there is 1 response, an additional 13 participants may be treated to collect more data. At the end of Stage 2, if there is 1 or no response, further clinical development may not be warranted. If there are 2 or more responses, it may show evidence of treatment efficacy.

Table 10.1.3.1-1: Example of a 2-stage Design Characteristics

Treatment	Indication	Historic/Target Rate (%)	Stage	Cum Sample Size	Conclude Inefficacy if R ^a	Conclude Efficacy if R ^a	PET ^b for Futility (%)	PEE ^c for Efficacy (%)
BMS-986207	CRC (nonMSI-H)	2/20	1	11	0	≥ 2	80	68
			2	24	≤ 1	≥ 2		
BMS-986207 and nivolumab	HCC, ovarian cancer	10/30	1	15	≤ 1	≥ 4	55	70
			2	26	≤ 5	≥ 6		
	CRC (nonMSI-H)	2/30	1	7	0	≥ 2	87	67
			2	15	≤ 1	≥ 2		

Abbreviations: BMS = Bristol-Myers Squibb, CRC, colorectal cancer; FNR, false-negative rate; FPR, false-positive rate; HCC, hepatocellular carcinoma; nonMSI-H, nonmicrosatellite instability-high; PEE, probability of early efficacy; PET, probability of early termination

^a R is the cumulative number of responses at the end of stage; all FPRs and FNRs < 10%

^b Probability of early termination if the historic rate is true

^c Probability of early efficacy signal if the target rate is true

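### HCC and ovarian cohorts: no rule says which stage decides when the two stages disagree, and the stated false-negative rate below 10% fails whichever stage decides

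*Combined protocol and SAP*

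**What the plan says.** Section 10.1.3.1 uses a Fleming two-stage design to guide Parts 2A and 2B and sizes each expansion cohort for an FPR and an FNR each below 10%. The HCC/ovarian stage-1 row of Table 10.1.3.1-1 reads "HCC, ovarian cancer 10/30 1 15 ≤ 1 ≥ 4 55 70": historic and target response rates of 10% and 30%, 15 participants, inefficacy at 1 or fewer responses, efficacy at 4 or more. The stage-2 row has 26 participants cumulatively, inefficacy at 5 or fewer and efficacy at 6 or more.

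The lower cut-offs at both stages sit under the heading "Conclude Inefficacy if R", and the upper ones under the matching heading for efficacy. Footnote a says "R is the cumulative number of responses at the end of stage; all FPRs and FNRs < 10" (percent).

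On conduct, the section says "There will be no stopping of a disease cohort for efficacy, although an early plan for the next stage of clinical development may be initiated", and also "Enrollment may continue into Stage 2, while the planned number of participants for Stage 1 are followed for efficacy evaluable tumor assessments". On status, the characteristics, "as an example, are provided in Table 10.1.3.1-1, although this is not used for statistical hypothesis testing".

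The only worked example is CRC monotherapy. Sections 10.3.1 and 10.3.8 give estimation methods and plan an interim analysis, but neither says what follows if the two stages disagree.

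**The concern.** In a two-stage design that ends at a stage-1 efficacy conclusion, a cohort that has passed stage 1 never reaches the stage-2 cut-off. Here the cohort carries on. Because R is cumulative and the final bar (6) is higher than the stage-1 bar (4), a cohort can pass the first and fail the second. The CRC rows avoid this because their efficacy cut-off is 2 at both stages.

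Two things are at stake. First, a stage-1 pass may start planning of the next development step, and the table's own last line may then say the opposite. Second, the row's error rates cannot be stated until the deciding stage is named, yet the table states them, and the section uses them as the basis for sample size.

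**Working it through.** **Inputs** (all from Table 10.1.3.1-1): p0 = 0.10, p1 = 0.30; stage 1 n = 15, futility at ≤ 1, efficacy at ≥ 4; cumulative n = 26, efficacy at ≥ 6. Stage 2 adds 26 − 15 = 11. Let X1 ~ Bin(15, p) and X2 ~ Bin(11, p), independent.

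**Plan's own figures.** Footnote b defines the futility figure as "Probability of early termination if the historic rate is true": P(X1 ≤ 1 | 0.10) = 54.9%, stated 55. Footnote c defines the other as "Probability of early efficacy signal if the target rate is true": P(X1 ≥ 4 | 0.30) = 70.3%, stated 70. Both reproduce.

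**Overlap.** Both conclusions apply when X1 = 4 and X2 ≤ 1, or X1 = 5 and X2 = 0:

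P(both) = P(X1=4)·P(X2≤1) + P(X1=5)·P(X2=0)

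- p = 0.10: 0.0428 × 0.6974 + 0.0105 × 0.3138 = 0.0299 + 0.0033 = 3.3%
- p = 0.20: 0.1876 × 0.3221 + 0.1032 × 0.0859 = 0.0604 + 0.0089 = 6.9%
- p = 0.30: 0.2186 × 0.1130 + 0.2061 × 0.0198 = 0.0247 + 0.0041 = 2.9%

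The same sum gives 6.4% at 15% and 5.1% at 25%.

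**Rule A: the stage-1 conclusion stands.**

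P(efficacy) = P(X1≥4) + P(X1=2)·P(X2≥4) + P(X1=3)·P(X2≥3)

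- p = 0.10: 0.0556 + 0.2669 × 0.0185 + 0.1285 × 0.0896 = 0.0720, so FPR 7.2%
- p = 0.30: 0.7031 + 0.0916 × 0.4304 + 0.1700 × 0.6873 = 0.8594, so FNR 14.1%

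**Rule B: the cumulative count decides, with the stage-1 futility stop kept.** This equals Rule A minus P(both).

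- p = 0.10: 0.0720 − 0.0332, about 0.039, so FPR 3.9%
- p = 0.30: 0.8594 − 0.0288 = 0.8306, so FNR 16.9%

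**Does ignoring the futility stop rescue the 10%?** No. It adds 0.0068 to power at p = 0.30, which gives FNR 13.4% under A and 16.3% under B.

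**CRC rows.** Two responses at stage 1 guarantee at least two at the end, so A and B coincide.

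- Monotherapy, p = 0.20: 0.6779 + 0.2362 × 0.9450 = 0.9011, FNR 9.9%; FPR at 2% is 6.1%
- Combination, p = 0.30: 0.6706 + 0.2471 × 0.9424 = 0.903, FNR 9.7%; FPR at 2% is 2.6%

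| Row | Deciding rule | FPR | FNR | Both below 10%? |
|---|---|---|---|---|
| HCC/ovarian | A | 7.2% | 14.1% | No |
| HCC/ovarian | B | 3.9% | 16.9% | No |
| CRC monotherapy | either | 6.1% | 9.9% | Yes |
| CRC combination | either | 2.6% | 9.7% | Yes |

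**The case against.** The strongest reply is that nothing here is binding. The framework is a guide, the table is an example outside hypothesis testing, and the assumed rates may be revised. Section 10.3.8 says no formal inference requiring adjustment will be made. Section 10.1.3.1 and footnote c already call the stage-1 result an early signal, and the consequence is only that planning may begin. An early look without stopping will sometimes be weakened by later data. All of this stands, and it makes the overlap minor. It does not settle which stage decides, because both stages share the same column headings. The CRC worked example, where one response at stage 1 leads to further enrolment before stage 2 is read, fits the reading that stage 2 serves undecided cohorts; the ban on efficacy stopping fits the reading that the final count governs.

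A reader might infer that the conflict inflates false positives beyond the plan's limit. It does not: the FPR is below 10% under both rules. A reader might also take alarm that, at a true rate of 10%, about 60% of stage-1 signals end in the inefficacy row (0.0332 / 0.0556). That is a share of an event with probability 5.6%, and comes to 3.3% of cohorts.

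Non-binding status does not excuse the error-rate statement. It is a stated property of the listed cut-offs and the stated basis for cohort size, and for this row it is wrong.

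**Conclusion.** The point holds in a limited form. The two conclusions can coincide for HCC and ovarian cohorts only, in at most about 7% of cohorts at the true rates computed between 10% and 30%. That is a gap in wording within a non-binding guide, not a flaw that invalidates the design. The documents do not support reading it as a breached false-positive limit or as contradictory formal tests.

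The firmer finding is that this row misses the stated FNR limit under either deciding rule (14.1% or 16.9%), while both CRC rows meet it. Naming the deciding stage moves the FPR by 3.3 points and power by 2.9 points, but neither choice brings the FNR below 10%.

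These figures assume independent responses with a constant rate, the tabulated sample sizes reached exactly, and 26 participants assessed as one cohort. The reproduced 55% and 70% indicate that the plan's stage-1 figures rest on the same binomial model.

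**What to change.** State in Section 10.1.3.1 which stage decides for HCC and ovarian cancer, by one of two routes:

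1. The cumulative count is final (6 or more of 26), and the stage-1 entry of 4 or more of 15 is relabelled as an early signal for planning. Print FPR 3.9%, FNR 16.9%.
2. The stage-1 conclusion stands, and the 5-or-fewer-of-26 line applies only to cohorts with 2 or 3 responses in 15. Print FPR 7.2%, FNR 14.1%.

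In either case, correct footnote a and the matching sentence in Section 10.1.3.1, so that the claim of both rates below 10% no longer covers this row.

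Lowering the final cut-off to 5 of 26 is not a substitute. It brings the FNR to 8.3% (Rule A) or 8.7% (Rule B) but raises the FPR to 11.8% or 10.5%. Keeping both limits would mean redesigning the row, which is a larger change than this point requires.

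The cost is wording in one paragraph, one table row and one footnote, with no change to sample size. The printed FNR becomes less favourable than the one now stated, and route 1 has about 3 points less power than route 2 (83.1% against 85.9%).

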4. OBJECTIVES AND ENDPOINTS

The objective and endpoints for this study are shown in Table 4-1.

Table 4-1: Objectives and Endpoints

Objectives	Endpoints

Primary
 
Part 1A, 1B, 2A, and 2B: To characterize the safety, tolerability, DLTs, and MTD/RP2D of BMS-986207 administered as monotherapy and in combination with nivolumab in participants with advanced solid tumors.Part 1C: To characterize the safety, tolerability, and DLTs of BMS-986207 in combination with nivolumab and ipilimumab in participants with advanced solid tumors.Part 2C: To evaluate the preliminary efficacy and safety of BMS-986207 in combination with nivolumab and ipilimumab in previously untreated participants with NSCLC whose tumors express $\geq 1\%$ PD-L1 based on PD-L1 IHC results from central testing.	
Incidence of AEs, SAEs, AEs meeting protocol-defined DLT criteria, AEs leading to discontinuation, and death; Incidence of laboratory abnormalities.Incidence of AEs, SAEs, AEs meeting protocol-defined DLT criteria, AEs leading to discontinuation, and death; Incidence of laboratory abnormalities.ORR, mDOR, and PFSR at 24 weeks by RECIST v1.1 by Investigator; Incidence of AEs, SAEs, AEs leading to discontinuation, and death.

Table 4-1: Objectives and Endpoints

Objectives	Endpoints
Secondary 
To assess the preliminary efficacy of BMS-986207 alone and in combination with nivolumab, in advanced solid tumors (Parts 1A, 2A, 1B, and 2B) and in combination with nivolumab and ipilimumab in advanced solid tumors (Part 1C).To characterize the PK and immunogenicity of BMS-986207 when administered alone, in combination with nivolumab or in combination with nivolumab and ipilimumab.	
ORR, mDOR, and PFSR at 24 weeks by RECIST v1.1Summary measures of PK parameters of BMS-986207 and incidence of ADA to BMS-986207

Abbreviations: ADA, anti-drug antibody; AE, adverse event; DLT, dose limiting toxicity; IHC, immunohistochemistry; mDOR, median duration of response; MTD, maximum tolerated dose; NSCLC, non-small cell lung cancer; ORR, objective response rate; [REDACTED] PD-L1, programmed death ligand 1; PFSR, progression-free survival rate; PK, pharmacokinetic; RECIST, Response Evaluation Criteria in Solid Tumors; [REDACTED] RP2D, recommended Phase 2 dose; [REDACTED]
[REDACTED] SAE, serious adverse event; [REDACTED].

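### Table 10.1.3.1-1 states that every false-negative rate is below 10%, but the HCC/ovarian row has a false-negative rate of about 14%

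*Combined protocol and SAP*

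**What the plan says.** Section 10.1.3.1 sets the framework: "The Fleming 2-stage design framework will be used as a guide for the expansion cohorts in Parts 2A and 2B". It says that each cohort's total sample size is to be calculated to give a "reasonable false-positive rate (FPR) <10% and false-negative rate (FNR) < 10" (percent), based on the assumed historic and target response rates. Table 10.1.3.1-1 then gives designs for three settings, and footnote a says of all of them: "R is the cumulative number of responses at the end of stage; all FPRs and FNRs < 10" (percent).

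The HCC/ovarian row reads as follows:

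- Historic rate 10%, target rate 30%.
- Stage 1, n = 15: conclude inefficacy at ≤1 response and efficacy at ≥4.
- Stage 2, cumulative n = 26: conclude inefficacy at ≤5 and efficacy at ≥6.
- Probability of early termination (PET) 55% at the historic rate; probability of an early efficacy signal (PEE) 70% at the target rate.

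The text leaves some freedom in how the stage 1 cutoffs are used. On futility: "Using a 2-stage design provides an option to stop early for futility", and, in the CRC monotherapy illustration, "the cohort may be stopped for futility". On efficacy: "There will be no stopping of a disease cohort for efficacy". The table is offered as an example, "although this is not used for statistical hypothesis testing".

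**The concern.** The error rates are the stated basis for the size of each expansion cohort. A reader of the footnote would take it that a combination with a true response rate of 30% in HCC or ovarian cancer would be missed fewer than 1 time in 10. A final requirement of 6 responses in 26 looks demanding for that: the expected count at 30% is 26 × 0.30 = 7.8, so results of 5 or fewer are not rare. If the false-negative rate (FNR) is higher than stated, a negative result in either cohort would be read as stronger evidence of inactivity than it is.

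**Working it through.** **Inputs**, all from the HCC/ovarian row: p0 = 0.10, p1 = 0.30, n1 = 15, n2 = 26 − 15 = 11. X1 and X2 are the responses in the first 15 and the next 11 participants, independent binomials.

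**Reproducing the printed figures**

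- PET = P(X1 ≤ 1 | 0.10) = 0.2059 + 0.3432 = 0.549 (printed 55%).
- PEE = P(X1 ≥ 4 | 0.30) = 0.703 (printed 70%).

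Both match, so the row has been read correctly.

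**FNR with the cutoffs as printed**, at p = 0.30. The design fails if stage 1 gives ≤1, or if stage 1 gives 2 or 3 and the total stays at ≤5:

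FNR = P(X1 ≤ 1) + P(X1 = 2)·P(X2 ≤ 3) + P(X1 = 3)·P(X2 ≤ 2)

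- P(X1 ≤ 1) = 0.0353
- P(X1 = 2)·P(X2 ≤ 3) = 0.0916 × 0.5696 = 0.0521
- P(X1 = 3)·P(X2 ≤ 2) = 0.1700 × 0.3127 = 0.0532
- FNR = 0.0353 + 0.0521 + 0.0532 = **0.1406**, so power is 85.9%.

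**False-positive rate (FPR)**, at p = 0.10:

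FPR = P(X1 ≥ 4) + P(X1 = 2)·P(X2 ≥ 4) + P(X1 = 3)·P(X2 ≥ 3) = 0.0556 + 0.0050 + 0.0115 = **0.072**

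**Other readings the text allows**

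The futility stop is optional, and a stage 1 result of ≥4 may or may not count as a final positive conclusion. The last column is the true response rate at which FNR would be 10%.

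| Reading | FPR | FNR | Response rate for FNR = 10% |
|---|---|---|---|
| As printed | 7.2% | 14.1% | 32.0% |
| Futility not enforced; stage 1 ≥4 stands | 7.3% | 13.4% | 31.7% |
| Futility enforced; only the final cutoff decides | 3.9% | 16.9% | 33.1% |
| Futility not enforced; only the final cutoff decides | 4.0% | 16.3% | 32.8% |

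**The other rows, by the same method**

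| Row | PET (printed) | PEE (printed) | FPR / FNR, futility enforced | FPR / FNR, not enforced |
|---|---|---|---|---|
| CRC monotherapy, 11 then 24 | 80.1% (80) | 67.8% (68) | 6.1% / 9.9% | 8.3% / 3.3% |
| CRC combination, 7 then 15 | 86.8% (87) | 67.1% (67) | 2.6% / 9.7% | 3.5% / 3.5% |

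The early-efficacy cutoff makes no difference in these two rows, because both stages use ≥2. Both rows satisfy the footnote, so the method is consistent with the rest of the table.

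**Could one cutoff be a misprint?** All combinations at 15 then 26 were searched: futility cutoff none or 0 to 14; early-efficacy cutoff none or any value above futility up to 15; final cutoff 1 to 26. Of 3,926 sets, none gives both rates below 10%. The closest is futility ≤1, no early efficacy and final ≥5, with FPR 10.5% and FNR 8.7%. The footnote therefore cannot hold at these sizes, whichever cutoff is changed.

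**The case against.** The arithmetic is not in dispute; the case on the other side concerns weight. The sample-size sentence is forward-looking and states an aim. The section says the assumed rates may change and that sizes may need to be increased. The table is labelled an example, is used as a guide and is not for hypothesis testing. Decisions are to rest on all available data, so a miss rate computed from the cutoffs is not literally the probability of abandoning an active combination. For Part 2B, response rate falls under a secondary objective ("To assess the preliminary efficacy of BMS-986207 alone and in combination with nivolumab, in advanced solid tumors (Parts 1A, 2A, 1B, and 2B"), and its planned analysis is an estimate with an exact 95% confidence interval.

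All of this stands, and it keeps the point minor. It does not rescue the footnote, which states computed properties of specific printed cutoffs at specific printed rates. Possible later changes to the assumptions do not alter what those cutoffs deliver. Nor is the row purely illustrative: section 10.1.3 says cohort size is based strictly on efficacy, and the 41 participants planned for Part 2B in section 5.2 equal 26 + 15, the two combination-row totals in the table.

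It could also be said that the table's own columns define a single reading (FPR 7.2%, FNR 14.1%), so the alternatives are unnecessary. They are needed only because the text makes futility stopping optional and rules out stopping for efficacy. Under each of them the conclusion is the same.

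**Conclusion.** The concern holds. Footnote a is wrong for the HCC/ovarian row: FNR is 14.1% with the cutoffs as printed, about 4 percentage points above the stated limit, and 13.4% to 16.9% across the four readings. A true 30% response rate would fall short of the cutoffs about 1 time in 7, or about 1 in 6 if only the final cutoff decides. The FPR half of the footnote holds in this row (3.9% to 7.3%), and both CRC rows meet both limits. The result rests on exact binomial probabilities at the printed rates, sizes and cutoffs, with no outside figure. Severity is minor; confidence is high.

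**What to change.** 1. State in section 10.1.3.1 whether a stage 1 result of ≥4 counts as a positive conclusion or only the final cutoff decides, and whether the futility stop is enforced.
2. Correct footnote a for the HCC/ovarian row to match. If stage 1 ≥4 counts: FPR about 7%, FNR about 14% (about 13% if futility is not enforced). If only the final cutoff decides: FPR about 4%, FNR about 17% (about 16% if futility is not enforced).
3. Add one sentence to section 10.1.3.1 saying that the FNR aim of below 10% is not met for HCC/ovarian at these sizes, so that the sample-size statement and the table agree.

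The cost is a one-line footnote correction and a short clarification in the text. One stated design property becomes less favourable; no cutoff, sample size or conduct changes.

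For information only: with every printed cutoff kept, a cumulative n of 30 meets both limits under all four readings (FPR 6.8% to 9.9%, FNR 6.8% to 9.3%). A cumulative n of 29 fails one of them (FNR 10.7% with futility enforced and only the final cutoff deciding). Choosing 30 would add 4 participants to each cohort under this row that reaches stage 2, and the enrolment totals in section 5.2 would then need revisiting. The correction does not depend on it.
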